1 BACKGROUND AND RATIONALE

Sporting activity is characterized by factors of the type, duration and intensity of exertion. Depending on the extent of these factors and the associated recovery time, damage to the muscles, signs of inflammation and fatigue in the nervous system occur, as well as energy substrate degradation and local swelling. Therefore, rapid regeneration after intensive sports has become all the more important. According to the meta-analysis by Bleakley et al. 2012, cold is considered one of the most effective recovery methods after sporting activity to delay delayed onset muscle soreness (DOMS). The DOMS are microscopic tears in muscle tissue called exercise-induced muscle damage, which can lead to delayed onset muscle soreness. DOMS usually peak between 24 and 48 hours – sometimes up to 72 hours – after exercise and are characterized by muscle shortening, increased passive stiffness, swelling, decrease in strength and power, localized muscle soreness, and altered proprioception.

The physiological background of cryotherapy is based on the removal of body heat by reducing tissue temperature. This is reflected in a reduced perception of muscle pain, so that the body feels more "awake" after training and causes less fatigue. In addition, due to the cold, the body lowers the heart rate and cardiac output, inducing vasoconstriction. The results are smaller vessel diameters, a reduced incidence of oedema and an improved oxygen supply to the cells. In order to maintain the body's core temperature, the central metabolism also increases, which promotes the transport of waste products. All these effects, in combination, could reduce the inflammation caused by exercise by reducing the death or damage of hypoxic cells and minimizing damage to secondary tissues by reducing the infiltration of leukocytes and monocytes. (Bleakley et al. 2012, Hohenauer E et al. 2015, Hubbard et al. 2004, Ostrowski et al 2018). Postoperative cryotherapy using ice packs, cooling, or continuous cryotherapy devices reduced pain scores on the visual analogue scale and analgesic consumption in about half of the prior art research studies comparing these outcomes to the control group (no cryotherapy) (11 [44%] of 25 studies on pain and 11 [48%] of 23 studies on opioids). However, an effect in increasing range of motion (3 [19 %] out of 16) or reducing swelling (2 [22 %] out of 9) was reported less frequently. (Kunkle et al. 2021). The study induced here is intended to provide new data, especially in the reduction of swelling and inflammation values, and to confirm the reduction of pain by cold application of the Axanova Cold Hot Pearls Maxi Pack.

2 INVESTIGATION OBJECTIVES AND DESIGN

2.1 Hypothesis and primary objective

The aim of this study is to investigate whether repeated, local cold applications have a positive impact on recovery compared to no intervention. Furthermore, it will be investigated whether cooling, which has been carried out immediately after the exertion, has a more positive influence on the recovery compared to refrigeration that has started 24 hours after the exertion. The ability to recover is determined on the basis of the following parameters: muscle soreness, inflammation levels, muscle swelling and maximum voluntary isometric contraction of the thigh muscles.

- H0A: There is no significant difference between repeated cold applications and the control intervention in terms of recovery capacity.
- H1A: There is a significant difference between repeated cold applications and the control intervention in terms of recovery capacity.

- H0A: There is no significant difference between immediate cold applications and delayed cold applications in terms of recovery.

H1A: There is a significant difference between immediate cold applications and delayed cold applications in terms of recovery.

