
Risk / Benefit Assessment	In this examination, the risk can be classified as minimal. The product is applied as recommended by the manufacturer. The muscle soreness protocol is a protocol that has already been described in the scientific literature.
Objective(s)	The aim of this study is to investigate how local, repeated cold applications affect the recovery phase according to a muscle soreness protocol. Recovery is assessed at 24-hour intervals (up to 72 hours according to the muscle soreness protocol).
Endpoint(s)	
Primary endpoints:
 
 • Sore muscles (VAS 0 – 10 cm) • Inflammation levels (blood sinking velocity, C-reactive protein, creatine kinase) • Muscle swelling (in cm using ultrasound) • Maximum Voluntary Isometric Thigh Contraction (in kg) 
Secondary endpoints
 
 • Surface temperature of the skin (in °C) • Thermal Perception
Investigation Design	Randomized, controlled trial
Statistical Considerations	Repeated measure ANOVA, n=45 subjects
Inclusion- / Exclusion Criteria	
Inclusion Criteria
 
 • Young, healthy adults between the ages of 18 and 30 • No surgical interventions on the musculoskeletal system in the trunk area and lower extremities 
Exclusion criteria
 
 • Current pain conditions: Subjects with acute pain conditions. • Current inflammatory conditions: Presence of inflammation or known inflammatory diseases. • Medication intake (excl. anticonception drugs): Subjects taking medication, with the exception of anticonception drugs. • Pregnant subjects: Women who are pregnant or breastfeeding. • Competitive athletes: Test subjects who practice competitive sports. • Children/adolescents: Subjects under 18 years of age or over 30 years of age. • Non-intact skin conditions (e.g. psoriasis): Skin conditions, such as psoriasis or other non-intact skin conditions. • Known circulatory disorders: Presence of known circulatory disorders. • Cold allergy (Raynaud's syndrome): Allergy to cold or the presence of Raynaud's syndrome. • Previous operations on the upper body or legs: Operations in the areas of the body examined. • Disturbed perception in the thigh: Disturbances in the sensation of temperature or touch in the thigh area. • Diagnosed diseases: Presence of diagnosed diseases that could affect participation in the examination. • Smoking: When the subject smokes.

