2.2 Primary and secondary endpoints

Primary endpoints

Muscle soreness

A visual analogue scale (VAS) is used for the quantitative assessment of muscle soreness. The muscle soreness of the test subjects is measured on both ventral thighs in 90° knee flexion within 2 seconds. Participants perform a squat at a 90-degree angle and use a hand-held glide scale to choose a value between 0 and 10 cm, with 0 representing no discomfort and 10 representing maximum discomfort. This scale is designed without visible numerical indicators to minimize repetition bias. Measurements are taken during baseline and 24, 48, and 72 hours after the intervention. The examination staff records the selected value in centimetres to document the level of the muscle soreness symptoms felt ventrally.

Inflammation levels

The general inflammation values are determined on the basis of 3 parameters. These are the blood sinking rate, the C-reactive protein and the creatine kinase. These parameters are determined by means of a venous blood draw.

Muscle swelling

Swelling of the ventral thigh muscles is performed using ultrasound diagnostics. The test subjects are in a lying position. Subsequently, a cross-sectional image of the thigh muscles is created and the distance from the femur to the outer boundary of the muscles is measured.

Maximum voluntary isometric muscle contraction

This parameter is measured using an ergometer chair in 90° hip flexion. The test subjects have to try to stretch their thigh as much as possible for 3 seconds. The maximum deflection is used to determine the maximum voluntary isometric muscle contraction.

Secondary endpoints

Superficial skin temperature

The skin temperature of the thighs is measured using the iButton system. The sensors are glued to the skin and continuously measure the temperature of the skin. The data from the sensors is then read out on a computer. This measurement is started during the baseline survey, for the duration of the muscle soreness protocol, and up to 20 minutes after the muscle soreness protocol.

Thermal Perception

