4 STATISTICS AND METHODOLOGY

4.1. Statistical analysis plan and sample size calculation

Sample calculation

Before any data collection is carried out, case number planning and sample size calculation is necessary in order to obtain valid results. In clinical trials and animal experiments, this is even mandatory and is carefully reviewed before approval is granted (MDR, Annex XV, Chapter 1, Section 2.1, DIN EN ISO 14155:2021-05). Postoperative cryotherapy utilizing ice packs, cooling, or continuous cryotherapy devices reduced pain scores on the visual analogue scale and analgesic consumption in about half of the research studies comparing these outcomes against their control (no cryotherapy). The average initial VAS score after pain induction varies depending on the study and is an approximation of a baseline value of 4.73 ± 2.39 . A reduction in the VAS score after cold application was assumed to be an average of 47%. After taking into account the dropout rate of 10% and splitting into 3 randomized groups, a patient count of 15 subjects per study arm is considered statistically appropriate. The results were determined using the PASS 2023 version 23.0.1 software.

Numerical Results for Multiarm Tests for the Difference Between Treatment and Control Agents Assuming Equal Variance

Solve for:	Number of cases
Group distribution:	equal to ($N_c = N_1 = N_2 = \dots$)
Test Type:	T-Test
Hypothesis:	$H_0: \delta = 0$ vs. $H_1: \delta \neq 0$
Number of groups:	3
Bonferroni Correction:	none (divisor = 1)

Comparison	Target Strength	Real	Number of cases	Mean μ_i	Difference δ_i	Standard deviation σ	Alpha
Control			13	4,72		2,1	
vs. A	0,8	0,832 33	13	2,21	-2,51	2,1	0,05
vs. B	0,8	0,912 87	13	1,87	-2,85	2,1	0,05
Total	n/a	n/a	39	n/a	n/a	n/a	n/a

Comparison	The group involved in the comparison between the treatment and control shown in this report row. The comparison is made on the basis of the difference.
Test Strength	The desired test strength. Test strength is the probability of rejecting a false null hypothesis for this comparison. This test strength refers only to the comparison shown in this line.
Really. TS	The test strength that is really achieved.
N_i	The number of elements in the i th group. The total sample size is displayed in the last row of the column.
μ_i	The mean value of the i th group at which the test strength is calculated. The first row contains μ_c , the mean value of the control group.

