δ_i	The difference between the i th treatment agent and the control agent ($\mu_i - \mu_c$) for which the test strength is calculated.
σ	The standard deviation of the responses within each group.
Alpha	The probability of rejecting the null hypothesis that the control mean is equal to the treatment mean described in this row.

Summary statements

A parallel 3-group design (with a control group and 2 treatment groups) is used to test whether the mean for each treatment group is different from the mean of the control group ($H_0: \delta = 0$ versus $H_1: \delta \neq 0, \delta = \mu_i - \mu_c$). The hypotheses are evaluated using two two-sided, two-sample methods. Bonferroni-adjusted t-tests with the same variance and an overall (experimental) Type I error rate (α) of 0.05. The common standard deviation for all groups is assumed to be 2.1. The mean value of the control group is assumed to be 4.72. The treatment means 2.21 and 1.87 with at least 80% test strength to be detected in each case. For the test, the (same) group sample size needed for each of the three groups (control and treatments) is 13 (39 subjects in total). The group sample sizes were calculated using PASS 2023, version 23.0.1.

Sample size taking into account the dropout rate

Group	Dropouts Abandonment Rate	Number of cases/group	Number of cases with drop-out rate	Number of abandoned participants
1 - 3	10%	13	15	2
Total	n/a	39	45	6

Taking into account the drop-out rate

Taking into account a dropout rate of 10%, the group sizes in each study arm should be 15 subjects.

Statistical approach to examine the primary endpoints

The statistical analysis is performed using IBM SPSS Statistics (version 27, IBM Corp., Armonk, NY, USA) and the significance level is set to $p < 0.05$.

In order to be able to determine the differences between groups, a repeated ANOVA analysis is carried out with a factor of 1: time (baseline, 24 hours, 48 hours, 72 hours) and a factor of 2:

intervention (group A, group B, group C) for the recovery parameters (inflammation values, muscle swelling, muscle soreness data, maximum voluntary isometric muscle contraction).

The examination is discontinued if the participants are intolerant to the local cold application. Participants in the IC and DC groups are instructed to cancel a cooling session and contact their contact immediately if they experience symptoms such as severe pain/discomfort as a result of the cooling.

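### Six primary measures are each tested at p < 0.05 with no rule for what shows recovery; under an any-one reading the false-positive chance is about 11–26%, and the Bonferroni statements conflict

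*Combined protocol and SAP*

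**What the plan says.** The Synopsis and section 2.2 list four primary endpoints: soreness on the VAS, inflammation, muscle swelling and MVIC. Inflammation is not one number. The Synopsis has "Inflammation levels (blood sinking velocity, C-reactive protein, creatine kinase" and section 2.2 says "The general inflammation values are determined on the basis of 3 parameters". No section combines the three, so six measures are primary.

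Section 2.1 poses two questions, cooling against control and immediate against delayed cooling. Both concern recovery as a whole: "The ability to recover is determined on the basis of the following parameters: muscle soreness, inflammation levels, muscle swelling and maximum voluntary isometric contraction".

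For the analysis, section 4.1 says "In order to be able to determine the differences between groups, a repeated ANOVA analysis is carried out with a factor of 1: time", with intervention group as the second factor, "for the recovery parameters (inflammation values, muscle swelling, muscle soreness data, maximum voluntary isometric muscle contraction". The significance level is p < 0.05. No deciding ANOVA term, pairwise contrast, order of endpoints or correction across measures is given.

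The sample size in section 4.1 uses the VAS alone, with two comparisons against control. The table gives the Bonferroni correction as "none (divisor = 1". The summary below it describes "Bonferroni-adjusted t-tests with the same variance and an overall (experimental) Type I error rate" of 0.05 and adds "The treatment means 2.21 and 1.87 with at least 80% test strength to be detected in each case".

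**The concern.** Two analysts could follow this plan on the same data and disagree on whether cooling aids recovery. One might accept a single significant measure; another might require all six. One might read the group effect, another the interaction. With no rule fixed beforehand, the reading can be chosen once results are known, and the trial is unblinded.

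The readings differ greatly. If any one measure suffices, 5% per test is not 5% for the conclusion. If all six are required, error is at most 5% but power falls.

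Two related gaps sit in section 4.1. The multiplicity statement for the two VAS comparisons contradicts itself, so the stated power may not belong to the method named. The second hypothesis, immediate against delayed, has no power calculation.

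**Working it through.** **Inputs.** From section 4.1: SD 2.1; control mean 4.72; treatment means 2.21 and 1.87 (differences 2.51 and 2.85); 13 completers per arm, 15 recruited; alpha 0.05, two-sided. From section 2.2: six measures (1 + 3 + 1 + 1). Correlations between measures, and between times within a person, are not in the documents and are assumed.

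**1. The plan's own figures.** The standard error of a difference is 2.1 × √(2/13) = 0.824. The noncentralities are 2.51/0.824 = 3.05 and 2.85/0.824 = 3.46, with 24 df. Two-sided noncentral-t power at 0.05 is 0.83233 and 0.91287, exactly as printed. 13/0.9 = 14.4, so 15 per arm.

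**2. The same test with Bonferroni.** At 0.05/2 = 0.025 and n = 13, power is 74.0% and 85.0%. The printed figures are therefore unadjusted, and 80% is not met for the smaller difference under the method the summary names. With Holm on the two comparisons, simulation gives 81% and 88%.

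**3. Any one of six, no true effect.** Independent measures: 1 − 0.95^6 = 26.5%. For six equally correlated statistics with correlation ρ and c = 1.96: 1 − ∫ φ(u) [Φ((c − √ρ·u)/√(1−ρ)) − Φ((−c − √ρ·u)/√(1−ρ))]^6 du.

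| Assumed correlation | Six tests | Four tests (blood markers as one) |
|---|---|---|
| 0 | 26.5% | 18.5% |
| 0.5 | 20.7% | 15.6% |
| 0.9 | 10.8% | 9.4% |

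Simulating the planned ANOVA (15 per arm, four times, 10,000 runs) and using only the interaction gives 26.5%, 21.8% and 12.1% for six measures. Using only the group effect gives 26.0%, 21.8% and 11.5%.

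**4. All six required.** If each test had 80% power (only the VAS has planning values), joint power is 0.8^6 = 26% when independent, rising to about 68% at correlation 0.9.

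**5. Immediate against delayed.** The planning gap is 2.21 − 1.87 = 0.34 cm; noncentrality 0.34/0.824 = 0.41; power 6.8% at n = 13. The 95% CI half-width is 2.064 × 0.824 = 1.70 cm.

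**6. Cost of Holm across six, VAS interaction, n = 13.** The first Holm step is 0.05/6. Noncentrality is 13 × Σ(interaction effects²)/(2.1² × (1 − within-person correlation)), on 6 and 108 df, assuming sphericity and no baseline difference. The sum of squares is 3.63 if both cooled arms show their planning difference at 24, 48 and 72 h, and 6.18 if the delayed arm equals control at 24 h.

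| Within-person correlation | Both arms benefit throughout | Delayed arm equals control at 24 h |
|---|---|---|
| 0.3 | 83% → 60% | 98% → 90% |
| 0.5 | 94% → 81% | 99.8% → 98% |
| 0.7 | 99.7% → 98% | almost unchanged |

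The right-hand column fits section 2.3 better, since the delayed arm has no cooling on day 1.

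**7. Follow-up contrasts.** Simulation: 15 per arm, within-person correlation 0.5, immediate arm shifted 2 SD at every follow-up in all six measures, delayed arm equal to control, interaction gate at 0.05/6. Testing delayed against control at each of 24, 48 and 72 h at 0.05/6 gives at least one false claim in about 13% of trials (between-measure correlation 0) or 12% (0.5).

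**The case against.** **The any-one rule is hypothetical.** This stands. A reader might infer that the trial has a 26% error rate, or about 46% if either the group or the interaction test may count and the measures are independent. The documents support neither as the plan's actual error, because they state no such rule. What they support is that some rule must apply and none is given.

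**Six is a count, not the plan's wording.** The lists show four headings. But three markers without a combined score mean three tests, and four tests still give 9.4% to 18.5%.

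**The VAS is really the primary endpoint.** It drives the sample size, and the background speaks of confirming pain reduction. But no section ranks it first, and section 1 puts particular weight on swelling and inflammation.

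**Bonferroni is already specified.** Only for the two VAS comparisons with control, not across measures, and the table denies it.

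**The planning means favour delayed cooling.** A reader might infer a conflict with the aim of showing immediate cooling to be better. The formal hypotheses in section 2.1 are non-directional, so these means show no error.

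**The matters are separable.** Fair: the Bonferroni conflict and the missing power for immediate against delayed do not depend on the missing success rule. They are raised together because the same paragraphs of section 4.1 need rewriting.

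**Conclusion.** The concern holds as a missing decision rule. Six measures are primary, each is tested at p < 0.05, and no text says which results support either hypothesis. The 26%, 21% and 11% rest on an any-one reading, one test per measure, no true effect on any measure, and assumed correlations of 0, 0.5 and 0.9.

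The Bonferroni contradiction needs no assumption: 83% and 91% are unadjusted, and the adjusted method named in the summary gives 74% and 85%. For immediate against delayed cooling, a non-significant result would be nearly uninformative at the planning gap. This should be corrected before the data are seen.

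**What to change.** 1. **Success rule.** State that a cooling effect is claimed only for individual measures whose group-by-time interaction passes Holm across the six at overall 0.05. Name those measures in the conclusion, and make no general recovery claim beyond them.
2. **Contrasts, if they are also claims.** Define one contrast per measure and pair, for example mean follow-up change from baseline, tested at 0.05/6 after the interaction passes at 0.05/6. If each follow-up time is tested, divide further, to 0.05/(6 × 3) = 0.05/18. Both levels lean on the interaction gate and suit the case where one pair is equal throughout. If an arm differs at one time only, 7 of the 9 pair-by-time comparisons are null and the bound at 0.05/18 is 6 × 7 × 0.05/18 = 11.7%. Counting every measure, pair and time needs no such condition: 6 × 3 = 18 for one contrast per pair, 6 × 3 × 3 = 54 for three times.
3. **Alternative for the sponsor.** Name the VAS at one pre-stated time as sole primary, with each cooled arm against control under Holm (81% and 88% power at n = 13), and say what role the ANOVA keeps.
4. **Sample-size text.** Make the two Bonferroni statements agree. Restate power as 74% and 85% (Bonferroni) or 81% and 88% (Holm), or say that 83% and 91% are unadjusted.
5. **Immediate against delayed.** Report an estimate with a 95% CI, and draw no conclusion of no difference from p > 0.05.

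**Cost.** These are wording changes, with no added visits or measurements. Holm lowers power per measure: for the VAS, by 23 points in the least favourable case tabulated (83% to 60%) and about 8 points or fewer if the delayed arm equals control at 24 h. The VAS-only option demotes the swelling and blood measures and rests the claim on self-report in an unblinded trial. Keeping 80% under plain Bonferroni for the smaller VAS difference needs 15 completers per arm (81%), or 15/0.9 = 16.7, so 17 recruited.

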2.3 Investigation design

This study is a single-center, randomized, controlled trial with 3 arms. After the subjects have been admitted to the examination, they are divided into one of the 3 groups.

Group A: immediate cooling according to the muscle soreness protocol

Group B: delayed cooling according to the muscle soreness protocol (24 hours delayed)

Group C: Control group

This examination is a clinical trial of risk category A.

Group A: immediate cooling

In this group, cooling starts immediately after the muscle soreness protocol. Cooling is carried out 3 x /day both on the day of the muscle soreness protocol and for a period of 72 hours. Both thighs are cooled with the "Cold Hot Maxi Pack" from Axanova for a period of 20 minutes.

Cooling log: Day 1 (muscle soreness log, 3x/day), Day 2 (3x/day), Day 3 (3x/day), Day 4 (3x/day)

Group B: delayed cooling

In this group, cooling starts 24 hours after the sore muscle protocol. Cooling is also carried out 3 x /day for a period of 72 hours. Both thighs are cooled with the "Cold Hot Maxi Pack" from Axanova for a period of 20 minutes.

Cooling log: Day 1 (muscle soreness log, no cooling), Day 2 (3x/day), Day 3 (3x/day), Day 4 (3x/day).

Group C: Control group

This group receives according to the muscle soreness protocol and will not receive any cooling intervention, nor any other intervention, for the entire period thereafter.

Sore muscle protocol

To induce sore muscles, the test subjects perform one-sided, 6 times 12 – 15 knee extensors on an ergometer chair. They straighten and bend the knee as far as possible. They repeated the exercise 5 more times after a 2-minute break (a total of 6 rounds). The movement sequences are observed and corrected if necessary. A similar protocol has already been successfully used in the literature to induce muscle soreness (Ruas et al 2022, Comparison between eccentric-only and coupled concentric-eccentric contractions for neuromuscular fatigue and muscle damage). In order to increase the significance of the investigation, the subjects are asked not to carry out any additional interventions during the experimental phase.

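### Immediate versus delayed cooling stands unranked under the primary objective, but the trial is sized only for each cooling arm against control on VAS soreness

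*Combined protocol and SAP*

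**What the plan says.** Section 2.1, whose heading covers both the hypothesis and the primary objective, gives two pairs of hypotheses. The first compares cooling with control: "H0A: There is no significant difference between repeated cold applications and the control intervention in terms of recovery capacity". The second compares the two cooling arms: "H0A: There is no significant difference between immediate cold applications and delayed cold applications in terms of recovery". Both pairs carry the same label, and nothing marks either as secondary. Recovery is defined there by soreness, inflammation levels, swelling and maximal isometric contraction.

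Section 4.1 sizes the trial on VAS soreness to "test whether the mean for each treatment group is different from the mean of the control group". The PASS table has one row for control versus A and one for control versus B, and none for A versus B. Of the planning means the summary says: "The treatment means 2.21 and 1.87 with at least 80% test strength to be detected in each case". The same section concludes that "a patient count of 15 subjects per study arm is considered statistically appropriate".

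The analysis in 4.1 is a repeated-measures ANOVA with time and group (A, B, C) as factors, at p < 0.05. It names no contrast or post hoc test for A versus B.

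Section 2.3 gives the cooling logs. Group A cools three times a day on Days 1 to 4. Group B's log runs "Day 1 (muscle soreness log, no cooling), Day 2 (3x/day), Day 3 (3x/day), Day 4 (3x/day").

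**The concern.** The question of when to start cooling is the only stated reason for having two cooling arms, and it appears in the trial's title. A reader of 2.1 will take it as one of two primary questions, and a reader of 4.1 will take 15 per arm as adequate for the trial's objectives. The calculation behind that number does not address the second question.

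At stake is what the trial can conclude about timing. If A and B differ by a modest amount, the comparison will most likely be non-significant, and nothing in the plan says how such a result is to be interpreted. Without a named contrast, the plan also does not say which number answers the second hypothesis: an omnibus group or time-by-group test does not isolate A from B.

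**Working it through.** **Inputs, all from section 4.1.** Control mean 4.72; treatment means 2.21 and 1.87; common SD σ = 2.1; two-sided two-sample t-test with equal variances; alpha 0.05 per comparison in the PASS table; n = 13 evaluable per arm, 15 enrolled after 10% dropout.

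**Method.** Exact t-test power. SE = σ√(2/n), noncentrality λ = δ/SE, df = 2n − 2, and power = P(|T′| > t₀.₉₇₅) with T′ noncentral t.

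- n = 13: SE = 2.1 × √(2/13) = 0.824; df = 24; critical t = 2.064.
- n = 15: SE = 2.1 × √(2/15) = 0.767; df = 28; critical t = 2.048.

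**Step 1: reproduce the plan's figures (n = 13).**

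- Control vs A: δ = 4.72 − 2.21 = 2.51; λ = 2.51/0.824 = 3.05; power 0.832 (plan: 0.83233).
- Control vs B: δ = 4.72 − 1.87 = 2.85; λ = 2.85/0.824 = 3.46; power 0.913 (plan: 0.91287).
- 13/(1 − 0.10) = 14.4, rounded up to 15.

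The plan's calculation is correct for what it covers, and it used alpha 0.05 without adjustment.

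**Step 2: A versus B on the same inputs.**

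| | n = 13 | n = 15 |
|---|---|---|
| Difference detectable with 80% power | 2.41 cm | 2.23 cm |
| Share of the assumed A-vs-control effect (2.51 cm) | 96% | 89% |
| 95% CI half-width, t × SE | 1.70 cm | 1.57 cm |
| Power for 2.21 − 1.87 = 0.34 cm | 6.8% | 7.1% |

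The 0.34 cm is only the gap between two planning means. For other differences at n = 13, power is 21% for 1.0 cm, 42% for 1.5 cm and 64% for 2.0 cm.

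**Step 3: sensitivity of the 0.34 cm result (n = 13 and n = 15).**

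- SD 2.39, the other value in 4.1: 6.4% and 6.6%.
- Error pooled over three arms: 6.9% and 7.2%.
- Alpha 0.025: 3.6% and 3.8%.
- Averaging the three post-exercise values, assumed correlation 0 to 0.9: about 7% to 12%.
- Baseline adjustment, assumed correlation 0 to 0.9: about 7% to 17%.

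The documents give no correlations, so the last two ranges are assumptions.

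**Step 4: alpha for the control comparisons.** The table's Bonferroni line reads "none (divisor = 1"), while the summary statement calls the t-tests Bonferroni-adjusted with an overall alpha of 0.05. At alpha 0.025 and n = 13, power is 74% for control vs A and 85% for control vs B.

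**Step 5: sessions in the logs.** A: 4 days × 3 = 12. B: 3 days × 3 = 9. The three-session gap arises on Day 1. It would remain if the Day 4 sessions fell after the 72-hour measurement and were left out (9 versus 6).

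**The case against.** The best defence is that 4.1 does not claim power for A versus B. The table notes tie each power to the comparison in its own row, and the summary restricts the calculation to treatment against control. This stands: it would be wrong to infer that the plan asserts 80% power for the timing question. What remains is that 2.1 gives that question equal rank and 4.1 calls the size appropriate without stating the limit.

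Several stronger readings are tempting and are not supported:

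- **That A versus B cannot be tested.** It can. Group is a three-level factor in the ANOVA and a contrast could be computed. What is missing is useful power on VAS and a specified contrast.
- **That power for the timing hypothesis is 7%.** That figure holds for VAS soreness only and for a difference nobody declared as a target. The means were chosen for comparisons with control, and they imply reductions of 53% and 60% from 4.72, not the 47% in the text. The same inputs would lead to about 600 per arm for 80% power, but that number rests on the same undeclared difference and should not be used as a requirement. The detectable difference of 2.2 to 2.4 cm does not depend on it.
- **That the plan assumes the opposite of its aim.** The lower mean (1.87) stands in row B, while 2.1 asks whether immediate cooling does better. But 4.1 never says that the labels in the PASS table are the trial's groups A and B. The power figures do not depend on the labelling.
- **That the sponsor will read non-significance as no effect of timing.** No text says so. The plan is silent, and that is the gap to close.

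The session count is a matter of interpretation, not of power. Section 2.1 defines delayed cooling by when it starts, so a comparison of regimens may well be intended.

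**Conclusion.** The point holds in this form: the timing comparison is unranked under the primary objective, is not covered by the sample size, and has no specified contrast. On VAS soreness, the trial would have 80% power only if the choice between immediate and delayed cooling mattered about 89% to 96% as much as cooling against nothing is assumed to matter. The 95% CI for A minus B would extend about 1.6 to 1.7 cm either side, so a result centred on zero could not exclude a difference of half the assumed cooling effect (2.51/2 = 1.26 cm).

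These figures assume the plan's SD of 2.1, 13 to 15 evaluable per arm, and a two-sample t-test at two-sided 0.05. The planned repeated-measures analysis could be somewhat more precise, depending on correlations that the plan does not give. Nothing can be said about power for inflammation markers, swelling or maximal contraction, for want of planning values. The control comparisons are correctly sized at unadjusted alpha.

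**What to change.** 1. **Section 2.1.** Label A versus B as secondary or exploratory, and give the two hypothesis pairs distinct labels. The alternative is to keep it primary with a justified target difference and a sample size to match, which may require more participants.
2. **Section 4.1, sample size.** State that it supports only A versus C and B versus C, on VAS soreness, by two-sample t-test at unadjusted two-sided alpha 0.05 (83% and 91% at 13 per arm). Reconcile this with the Bonferroni wording: if the adjustment is meant, the figures are 74% and 85% at alpha 0.025.
3. **Section 4.1, analysis.** Specify an A-minus-B contrast within the planned model, reported with a 95% CI (half-width about 1.6 to 1.7 cm on VAS). Describe it as a comparison of two cooling regimens, since the logs list 12 and 9 sessions, so a difference could not be put down to timing alone.
4. **Interpretation.** State that a non-significant A-versus-B result will not be read as equal effect.

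The cost of steps 1 to 4, with A versus B ranked below the control comparisons, is wording in two sections and one contrast. The claim on timing becomes less favourable. No more participants are needed.
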